## Duration of response

Among patients with a confirmed response (PR or CR), DOR is defined as the time from first documented response (PR or CR) to the date of first documented PD or death due to underlying cancer. If a patient has not had an event, DOR is censored at the date of last adequate tumor assessment.

The censoring and event date options to be considered for the main analysis are presented in [Table 2-1](#).

Table 2-1 Outcome and event dates for DOR and PFS analyses

	Situation	Date	Outcome
A	No baseline assessment	Date of first dose of study drug*	Censored
B	Progression at or before next scheduled Assessment	Date of progression	Progressed
C1	Progression or death after exactly one missing assessment	Date of progression (or death)	Progressed
C2	Progression or death after two or more missing assessments	Date of last adequate assessment†	Censored
D	No progression	Date of last adequate assessment •	Censored
E	Treatment discontinuation due to 'Disease progression' without documented progression, i.e. clinical progression based on investigator claim	N/A	Information ignored. Outcome derived based on radiology data only.
F	New anticancer therapy given	Date of last adequate assessment •	Censored
G	Deaths due to reason other than deterioration of 'Study indication'	Date of last adequate assessment •	Censored (only applicable to DOR)

• The rare exception to this is if the patient dies no later than the time of the second scheduled assessment as defined in the protocol in which case this is a PFS event at the date of death

• After the last adequate tumor assessment. "Date of next scheduled assessment" is defined in Section 3.2.7 of Section 14 (Appendix II) of the LDK378A2203 protocol

DOR will be described in tabular and graphical format using Kaplan-Meier methods including estimated median (in months) with 95% CI, 25th and 75th percentiles (Brookmeyer and Crowley 1982, Klein and Moeschberger 2005) and Kaplan-Meier estimated probabilities with confidence intervals (Kalbfleisch and Prentice 2002) at several time points (including at least 4, 8, 12, 15, 18 months).

These analyses will be performed separately based on investigator assessment and based on BIRC assessment.

Refer to Section 4.6.3 for further details regarding derivation of Kaplan - Meier estimates.

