- Section 8.1.3: updated with the list of adverse events of special interest
- Section 13: update to the list of references
- Appendix 14.1: table title for prohibited concomitant medications requiring caution has been updated with a notation for LDK378, deletion of CYP2C8 substrates and paclitaxel, and updated footnotes for clarification
- Appendix Table 14-2: list of medications to be used with caution updated with deletion of CYP2B6 and CYP2C8 substrates, clarithromycin and telithromycin
- Editorial and typographical changes throughout the document as required

IRB/IEC

A copy of this amended protocol will be sent to the Institutional Review Board (IRBs)/Independent Ethics Committee (IECs) and Health Authorities.

The changes described in this amended protocol require IRB/IEC approval prior to implementation. The changes herein affect the Informed Consent. Sites are required to update and submit for approval a revised Informed Consent that takes into account the changes described in this protocol amendment.

Updates to the safety data in the associated Informed Consent Form (ICF) to match the Investigator's Brochure Edition 7 (released on 12 Jun 2014) have been performed separately to this protocol on 15 Sep 2014.

Summary of previous amendments

Amendment 2

Amendment rationale

As of the release date of this amendment, 57 patients have been screened to the study. 45 patients have been treated.

This amendment has been implemented to address the availability of new safety data as represented in the latest Investigator Brochure, to amend the eligible study population, and to clarify sections of the protocol where additional guidance was required:

- Addition a secondary endpoint of overall intracranial response rate (OIRR) due to the interest in LDK378 activity in the brain
- Allowing pre-screening during prior chemotherapy treatment and prior to progression of disease
- Allowing the enrolment of chemotherapy-naïve patients to target the ALK-inhibitors-naïve population regardless of previous chemotherapy
- Update of safety data in the protocol and associated Informed Consent Form (ICF) to match the Investigator Brochure Edition 4 (release on 28 June 2013).
- Change in definition of duration of response (DOR) in response to health authority feedback and based on the advanced cancer under study and it being difficult to ascertain whether a death is due to the underlying cancer

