2.3 Rationale for dose and regimen selection

[REDACTED]

[figure not shown]
3 Objectives and endpoints

[figure not shown]
Objectives and related endpoints are described in [Table 3-1](#) below.

[figure not shown]
[REDACTED]

Table 3-1 Objectives and related endpoints

Objective	Endpoint	Analysis
Primary		
To demonstrate the antitumor activity of LDK378, as measured by overall response rate (ORR) to LDK378 by investigator assessment	ORR per RECIST 1.1 calculated as the proportion of patients with a best overall response defined as complete response or partial response (CR+PR) as assessed by investigator	Refer to Section 10.4.
Key secondary		
To evaluate response related endpoints as assessed by investigator and Blinded Independent Review Committee (BIRC):	The following endpoints will be evaluated by investigator assessment and BIRC per RECIST 1.1:	Refer to Section 10.5.1.
1. Duration of response (DOR)	1. DOR, calculated as the time from the date of the first documented CR or PR to the first documented progression or death due to any cause	
2. Disease control rate (DCR)	2. DCR, calculated as the proportion of patients with best overall response of CR, PR, or SD	
3. Time to Response (TTR)	3. TTR, calculated as the time from first dose of LDK378 to first documented response (CR+PR)	
4. Overall intracranial response rate (OIRR)	4. OIRR calculated as the ORR (CR+PR) of lesions in the brain for patients who have measureable disease in the brain at baseline	
And to assess:	And:	
5. ORR by BIRC assessment	5. ORR (CR+PR) per RECIST 1.1 as assessed by BIRC	
Other secondary		
1. To evaluate the safety profile of LDK378	1. Adverse events and laboratory abnormalities	Refer to Section 10.5.2.
2. To evaluate progression-free survival (PFS)	2. PFS, defined as time from first dose of LDK378 to progression or death due to any cause, as assessed by BIRC and investigator assessment	
3. To evaluate overall survival (OS)	3. OS, defined as time from first dose of LDK378 to death due to any cause	

Objective	Endpoint	Analysis
		

4 Study design

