10.5.1 Key secondary objective(s)

Duration of response

Among patients with a confirmed response (PR or CR) per RECIST 1.1, duration of response (DOR) is defined as the time from first documented response (PR or CR) to the date of first documented disease progression or death due to any cause. DOR will be listed by patient and may be described using Kaplan-Meier curves and relevant statistics if appropriate. Censoring rules for DOR are described in the Appendix II.

Time to response

Time to response (TTR) is defined as the time from the date of the first dose of LDK378 to first documented response (CR or PR, which must be confirmed subsequently) per RECIST

1.1. TTR will be described using Kaplan-Meier methods and appropriate summary statistics. The TTR analysis will be conducted with censoring rules as described in the [Appendix II](#).

Disease control rate

The disease control rate (DCR), defined as the proportion of patients with best overall response of CR, PR, or SD per RECIST 1.1 will be estimated and the 90% CI provided. DCR will be estimated.

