## 2.8 Analysis of secondary variables

### 2.8.1 Efficacy

All tumor response related endpoints under the secondary efficacy objectives (DOR, TTR, DCR, PFS) will be analyzed as per investigator assessment and as per the BIRC. Confirmation of response is required for all response endpoints, as per RECIST 1.1.

All secondary endpoint analyses will be performed based on the FAS, unless otherwise specified.

No adjustment for multiple testing will be made.

The key secondary efficacy endpoints are

- ORR by BIRC
- DOR by investigator assessment and by BIRC
- DCR by investigator assessment and by BIRC
- TTR by investigator assessment and by BIRC

Other secondary efficacy endpoints are

- PFS by investigator assessment and by BIRC
- OS

The definitions and details on the derivation of the secondary endpoints are given in the LDK378A2203 protocol. Further details and notes needed for programmatic implementation of RECIST 1.1 guidelines are provided in [Section 4.6.1](#).

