**Table 3-1 Changes to protocol specified analysis or descriptions and rationale**

Protocol Section	Protocol Description	Change	Rationale
Section 10.1.2-Safety Set	The Safety Set will include all patients who receive at least one dose of LDK378	Changed to "The Safety Set consists of all patients who received at least one	This change from the protocol wording for and has been introduced in Section 2.2 of the RAP for

Protocol Section	Protocol Description	Change	Rationale
	and have at least one valid post-baseline safety assessment. The statement that a patient has no AE (on the Adverse Event eCRF) constitutes a valid safety assessment.	dose of study drug"	program clarification/simplification. It does not constitute a de facto change given that the DAR eCRF where the information on dosing is collected will also collect the reason for why the drug was discontinued which in itself constitutes a safety assessment
Section 10.1.3 - Per Protocol Set	The PPS will include patients who have an adequate tumor assessment at baseline, a follow-up tumor assessment >8 weeks after starting treatment (unless disease progression is observed before that time), and no major protocol deviation"s	Changed to "The PPS will include patients who have an adequate tumor assessment at baseline a follow-up tumor assessment >7 weeks after starting treatment (unless disease progression is observed before that time), and no major protocol deviations"	This change was made to take into consideration the +/-1 week window associated with tumor assessments
Section 10.5.3.3 - Laboratory abnormalities	Frequency tables for newly occurring on-treatment grades 3 or 4 will be provided separately for hematology and biochemistry laboratory tests	Deleted	One of the proposed analysis described in Section 2.8.2 of the RAP under Laboratory Abnormalities, is a shift table using CTC grades to compare baseline to the worst post-baseline value on treatment. The information that would be contained in the tabulation described in the protocol is similar to that contained within this shift table
Section 10.4 -	Reference is made to	The analysis for the	This change is made given

Protocol Section	Protocol Description	Change	Rationale

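### The SAP ends duration of response only at cancer deaths and censors other deaths, against the protocol's any-cause definition and without declaring the change

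*SAP*

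**What the plan says.** **Protocol.** DOR is a key secondary endpoint. The objectives table (Protocol Table 3-1) ends it at "the first documented progression or death due to any cause", and Section 10.5.1 ends it at "the date of first documented disease progression or death due to any cause". Section 10.5.1 places the censoring rules in Appendix II, whose content is not visible in the public copy. Amendment 2 changed the definition from cancer death to any-cause death. It cited health authority feedback, the advanced cancer under study, and "it being difficult to ascertain whether a death is due to the underlying cancer".

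**SAP.** Section 2.8.1 defines DOR as "the time from first documented response (PR or CR) to the date of first documented PD or death due to underlying cancer". Table 2-1, which is stated to govern the main analysis, has a row G headed "Deaths due to reason other than deterioration of 'Study indication". That row censors such deaths at the last adequate assessment, for DOR only. The same section also says: "The definitions and details on the derivation of the secondary endpoints are given in the LDK378A2203 protocol". SAP Table 3-1, titled "Changes to protocol specified analysis or descriptions and rationale", covers the Safety Set, the Per-Protocol Set, a laboratory table and confidence levels. It has no entry for the DOR definition.

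**The concern.** The two documents give different events for the same endpoint. The SAP also contradicts itself, because it says that it takes its definitions from the protocol and then writes a different one.

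A programmer working from the SAP would censor a responder who dies of, say, pneumonitis or sepsis without progression. The same death would be an event for PFS. The DOR result would then rest on cause-of-death attribution, which Amendment 2 described as hard to make. Row G treats such deaths as non-informative, and toxic deaths may not be.

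Protocol Section 2.2 uses DOR to support the response rate, so a flattering DOR matters even without a test. SAP version 1.0 is dated 12 April 2018, after the final cut-off of 22 January 2018. An undeclared change to an endpoint at that point in an open-label single-arm study is hard to defend, even if it is accidental.

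**Working it through.** **1. Text comparison**

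| Source | Death that ends DOR | Other deaths |
|---|---|---|
| Protocol before Amendment 2 | Underlying cancer | Not counted as events |
| Protocol Table 3-1 and Section 10.5.1 (current) | Any cause | No such category |
| SAP 2.8.1 text | Underlying cancer | Not counted as events |
| SAP Table 2-1, row G | Study indication | Censored at last adequate assessment |
| SAP Table 3-1 (declared changes) | No entry | No entry |

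The SAP matches the superseded protocol text. Other SAP text is out of date in the same way. Section 1.1 still requires prior chemotherapy, which Amendment 2 dropped. Table 3-1 lists as changes the safety-set and 7-week wording that Amendment 1 had already put into the protocol. Stale text is therefore the likely cause, but this is inference.

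**2. Gap in Table 2-1.** Row B reads "Progression at or before next scheduled Assessment" and does not mention death. Row C1 covers death, but only after exactly one missed assessment. Row D, headed as no progression, would literally censor a death with no missed assessment. The table has no row that makes such a death an event.

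**3. Direction.** Take one non-cancer death with r patients at risk. Under the protocol, the Kaplan-Meier curve is multiplied by (1 − 1/r) at that death. Under row G that factor is absent, so from that date onward the SAP curve lies higher. If there is no such death, or if it is already censored under row C2 (two or more missed scans) or row F (new therapy), the two curves coincide.

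**4. Size (illustration).** The plan states no DOR figure to reproduce, and power for key secondary variables is marked not applicable in both documents. Inputs:

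- Median DOR of 8.2 months and 71% lasting at least 6 months (phase I, Protocol Section 1.2.1.2.2).
- f, the share of DOR events that are non-cancer deaths: not in the documents; assumed 1% to 15%.
- Proportional cause-specific hazards: assumed.

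Censoring a share f of events gives S_SAP(t) = S(t)^(1−f). For a Weibull with shape k, the median becomes 8.2 × (1−f)^(−1/k).

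Reading 71% as S(6), k = ln[0.693/(−ln 0.71)] / ln(8.2/6) = ln(0.693/0.342)/ln(1.367) = 2.26.

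The exponential (k = 1) implies S(6) = 0.5^(6/8.2) = 60%, not 71%, so it is an upper case.

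| f | Median, Weibull | Median, exponential | 12-month DOR, Weibull | 12-month DOR, exponential |
|---|---|---|---|---|
| 0 | 8.20 | 8.20 | 19.5% | 36.3% |
| 1% | 8.24 | 8.28 | 19.8% | 36.6% |
| 5% | 8.39 | 8.63 | 21.1% | 38.2% |
| 10% | 8.59 | 9.11 | 22.9% | 40.1% |
| 15% | 8.81 | 9.65 | 24.9% | 42.2% |

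On the assumption of 62 responders (50% of 124 treated), all with an event, f = 1% to 15% is 62 × 0.01 = 0.6 to 62 × 0.15 = 9.3 patients.

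**5. Simulation.** Exponential times, 8-weekly scans, non-cancer deaths censored at the last scan, 53 or 80 responders, f of 5%, 10% or 20%, 1,000 runs each. The SAP-rule median was higher than the any-cause median in 27% to 90% of runs, equal in the rest and lower in none. With 53 responders and f = 10%, the mean medians were 9.06 months (any cause) and 10.09 months (SAP rule). Both exceed 8.2 because progression is dated to the next scan.

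**6. Primary endpoint.** An exact binomial calculation for the two-stage design reproduces the stated success probabilities of 0.049, 0.268, 0.642 and 0.900. DOR does not enter them.

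**The case against.** **Appendix II is unseen.** The protocol puts the DOR censoring rules there, and the SAP says it implements that appendix. Row G may have been copied from it, in which case that part of the conflict lies inside the protocol. This stands as a reason to check the appendix before deleting the row. It does not rescue the SAP's definition sentence, which conflicts with Section 10.5.1 either way.

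**The row B and D gap is mostly wording.** The PFS text lists when PFS is censored, and a death with no missed scan is not on the list. Row G would be pointless if row D already censored all such deaths. This is fair: the intent can be recovered, and the gap is a clarification rather than the main fault.

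**The size rests on assumptions.** There is no source for f. The 8.2 months comes from another population: doses of at least 400 mg, 79 of 114 patients pretreated with crizotinib, RECIST 1.0. Its own 95% interval is 6.9 months to not estimable, and scans are 8 weeks apart. The Weibull shifts at f of 1% to 10% (0.04 to 0.39 months) are small beside both. This also stands; only the direction is firm.

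**DOR is descriptive.** It has no test and no power calculation. This SAP covers the final analysis only, and an earlier analysis plan that it cites is not shown. That limits the consequences, but it does not make an undeclared change to a key secondary endpoint acceptable.

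**Conclusion.** The concern holds. The SAP's main DOR analysis is not the protocol's endpoint, the change is undeclared, and it restores wording that the protocol had deliberately replaced. This follows from the text alone.

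Any effect on DOR is an overstatement, and it arises only if a responder dies of a non-cancer cause before documented progression and is not already censored under row C2 or F. The size cannot be fixed from the documents. Over the assumed range f = 1% to 15%, the shift in an 8.2-month median is 0.04 to 0.61 months (Weibull) or 0.08 to 1.45 months (exponential, upper case); it is zero at f = 0. The response rate, its decision rule and the sample size are untouched. The definition should be corrected before DOR is reported, because the endpoint is key secondary and the correction is cheap.

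**What to change.** 1. Check protocol Appendix II for a rule like row G. If there is one, reconcile it with the any-cause definition in Protocol Table 3-1 and Section 10.5.1.
2. In SAP 2.8.1, redefine the end of DOR as the earlier of first documented progression and death from any cause.
3. Delete row G of SAP Table 2-1.
4. Extend row B to progression or death, so that a death with no missed assessment is an event at the date of death for both DOR and PFS. Limit row D to patients with neither progression nor death.
5. Apply these rules to both the investigator and the BIRC analyses.
6. If the cancer-death version is wanted, keep it as a labelled supplementary analysis and enter it in SAP Table 3-1 with a reason.

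The cost is one sentence, three table rows (B, D and G), one programming flag and the Appendix II check. Reported DOR may come out slightly shorter.

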### Disease control rate

DCR, defined as the proportion of patients with BOR of CR, PR, SD, or Non-CR/Non-PD, per RECIST 1.1, will be estimated and the exact binomial 95% CI provided.

These analyses will be performed separately based on investigator assessment and based on BIRC assessment.

## Time to response

Time to overall response of CR or PR (TTR) is defined as the time from start of study drug to first documented response (CR or PR, which must be confirmed subsequently). Patients who did not achieve a response (i.e. confirmed response) will be censored as follows:

- At maximum follow-up (i.e. FPFV to LPLV used for the analysis), for patients who had a PFS event (i.e. progressed or died due to any cause). In this case the PFS event is the worst possible outcome as it means the patient cannot subsequently respond;
- At last adequate tumor assessment date, otherwise. In this case the patient has not yet progressed so he/she theoretically still has a chance of responding.

TTR will be summarized by frequency counts using descriptive statistics for patients with confirmed CR or PR. These analyses will be performed separately based on investigator assessment and based on BIRC assessment.

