1.2.1.2.2 Clinical efficacy

[figure not shown]
LDK378 has demonstrated potent antitumor activity in patients with advanced, ALK-rearranged NSCLC (Shaw et al 2013). Among 114 response-evaluable patients with at least 18 weeks of follow-up prior to 28 Feb, 2013, or who discontinued study earlier, and were treated with LDK378 doses of 400 mg qd or higher, 66 (58%) patients have responded (Table 1-2). In addition, the response rate to LDK378 is similar regardless of prior ALK inhibitor therapy. In patients with NSCLC treated at ≥ 400 mg qd, who had previously received crizotinib, the response rate was 57%, and in those who had not previously received crizotinib it was 60%. Post-baseline tumor measurements are available for 104 of the 114 response-evaluable patients. A waterfall plot displaying the maximum decrease from baseline in the sum of the longest tumor diameters (Figure 1-1) shows that the large majority of patients treated with LDK378 had a reduction in tumor burden. The median duration of response in

patients who responded and were treated at ≥ 400 mg qd was 8.2 months (95% CI: 6.9, not estimable), and 71% had a duration of response of 6 months or longer.

Table 1-2 Study CLDK378X2101 Response Rate

Response rate (RECIST v1.0)	N	CR n (%)	CR + PR n (%)
All NSCLC, ≥ 400 mg/d	114	1 (1)	66 (58)
NSCLC, at 750 mg	78	0	47 (60)
ORR by prior crizotinib treatment			
NSCLC prior crizotinib, ≥ 400 mg/d	79	1 (1)	45 (57)
NSCLC prior crizotinib, 750 mg/d	49	0	29 (59)
NSCLC crizotinib naïve, ≥ 400 mg/d	35	0	21 (60)
NSCLC crizotinib naïve 750 mg/d	29	0	18 (62)

[figure not shown]
Figure 1-1 Waterfall plot of reduction in sum of longest tumor diameters

[figure not shown]
[figure not shown]
The available data from the ongoing phase I study indicate that LDK378 has substantial antitumor activity in patients with ALK-rearranged NSCLC whose disease has failed crizotinib therapy or who are naïve to crizotinib therapy.

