## Best overall response

The BOR will be assessed based on reported lesion responses at different evaluation time points. Both CR and PR require confirmation at least 4 weeks after its initial observation.

Only tumor assessments performed before the start of any further anti-neoplastic therapies (i.e. any additional secondary anti-neoplastic therapy or anti-cancer surgery) will be considered in the assessment of BOR. If a patient receives any further anti-neoplastic therapy while on study, any subsequent assessments will be excluded from the BOR determination. Further anti-neoplastic therapies will be identified via protocol deviations or from the data collected on 'Anti-neoplastic therapies since last date of study drug' as appropriate. Clinical deterioration will not be considered as documented disease progression. Patients with BOR 'unknown' will be summarized by reason for having unknown status. The following reasons will be used:

- No valid post-baseline assessment
- All post-baseline assessments have overall response UNK
- New anti-neoplastic therapy started before first post-baseline assessment
- Stable disease (SD) too early ( $\leq 6$  weeks after start date of study drug)
- PD too late ( $> 12$  weeks after start date of study drug)

Special (and rare) cases where BOR is 'unknown' due to both early SD and late PD will be classified as 'SD too early'.

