## Progression-free survival

PFS is defined as the time from the start date of study drug to the date of the first radiologically documented PD or death due to any cause.

If a patient has not progressed or is not known to have died at the date of analysis cut-off or has received any further anticancer therapy, PFS will be censored at the date of the last adequate tumor evaluation before the cut-off date or before the start of the new anticancer therapy date, whichever is earlier. Clinical deterioration will not be considered as a qualifying event for progression. Refer to [Table 2-1](#) for censoring and event date options and outcomes for PFS.

In particular, PFS will be censored at the last adequate tumor assessment: **if** one of the following occurs: absence of event; the event occurred after a new anticancer therapy is given; the event occurred after two or more missing tumor assessments (see [Section 4.6.1](#)). See also [Section 4.6.1](#) describing the special case of a missing baseline tumor assessment.

PFS will be described in tabular and graphical format using Kaplan-Meier methods as described for DOR, including estimated median (in months) with 95% CI, 25th and 75th percentiles and Kaplan-Meier estimated probabilities with corresponding 95% CIs at several time points (including at least 4, 8, 12, 15 and 18 months). Censoring reasons will also be summarized.

These analyses will be performed separately based on investigator assessment and based on BIRC assessment.

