#### 4.6.3 Kaplan-Meier estimates

To analyze time to event variables (DOR, TTR, OS and PFS) an estimate of the survival function will be constructed using *Kaplan-Meier (product-limit) method* as implemented in PROC LIFETEST with METHOD=KM option (see example below). The median time to event and estimated event rates at different time points will be estimated, along with associated 90% or 95% two-sided CIs derived based on the complementary log-log

transfonnation. This will be conducted via the SAS procedure LIFETEST. The TIME statement will include a variable with survival times (*survtllle* in the example below) and a (iight) censoling variable (*ensor* in the example below) with a valtle of 1, representing censoring (example code below for constmction of 90% CIs):

```
PROC LIFETEST data = dataset
  METHOD = KM
  ALPHA = 0.1
  ALPHAQT = 0 .1
  CONFTYPE=LOGLOG ;
TIME survtime*ensor(1) ;
RUN;
```

*/\* survtime* represents variable containing event/censor times;  
*ensor* represents censoiing variable (1 = censored, 0 = event); \*/

Kaplan-Meier sUtv iv aJ and failure fmcion estimates from this procedure will be used to construct the Kaplan-Meier figures

Median smvival will be obtained along with 2-sided 90% or 95% CIs calculated from PROC LIFETEST output using the method ofBrookmeyer & Crowley, 1982.

Kaplan-Meier estimates with 2-sided 90% or 95% Cis at sp ecific tim e points will be summarized. The time points can be expressed in weeks or in months depending on the time- to-event variable. The Cis will be constmcted using Greenwood's foImula [Collet , 1994 , p.23] for the standard enor of the Kaplan-Meier estimate.

The Kaplan-Meier graphs will be constncted usingSAS software.

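### The time-to-response rule censors non-responders who start new anticancer therapy as if they could still respond, so a Kaplan-Meier response curve can overstate the proportion responding

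*SAP*

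**What the plan says.** SAP 2.8.1 (Time to response) gives two censoring rules for patients without a confirmed response.

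- Censoring at maximum follow-up applies "for patients who had a PFS event (i.e. progressed or died due to any cause"), because such a patient cannot respond later.
- Everyone else is censored as follows: "At last adequate tumor assessment date, otherwise". The reason given is: "In this case the patient has not yet progressed so he/she theoretically still has a chance of responding".

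Three other places bear on who falls under the second rule.

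- SAP 2.8.1 (Best overall response): once further anti-neoplastic therapy starts, "any subsequent assessments will be excluded from the BOR determination".
- SAP 2.8.1 (Progression-free survival) lists, among the situations in which PFS is censored, "the event occurred after a new anticancer therapy is given; the event occurred after two or more missing tumor assessments". Table 2-1 repeats this in row F (new anticancer therapy) and row C2 ("Progression or death after two or more missing assessments").
- SAP 2.7.2 and 2.7.3: ORR is computed on the full analysis set, and patients with an unknown or unassessed best response count as non-responders.

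On the output, the TTR text ends with a descriptive summary in confirmed responders only. SAP 4.6.3, however, begins "To analyze time to event variables (DOR, TTR, OS and PFS) an estimate of the survival function will be constructed" by the Kaplan-Meier method, and protocol 10.5.1 also plans Kaplan-Meier for TTR. SAP Table 3-1, which lists changes from the protocol, does not withdraw that plan.

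**The concern.** The two-part rule is sensible in principle. Patients who can no longer respond stay in the denominator, and patients who still might respond are censored. The fault is that a PFS event is used as the marker for no longer being able to respond, and it misses some of those patients.

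A non-responder who starts new therapy before documented progression cannot become a responder under the SAP's own rule for best overall response, and has no PFS event. The patient is therefore handled as ordinary censoring, although the new therapy acts as a competing event. Table 2-1 row E feeds this group: clinical progression without radiological evidence is ignored, so a patient who stops for that reason and moves to another therapy arrives at row F. In the BIRC version, protocol 7.2.1.2 lets scans stop once the investigator calls progression and the drug ceases. A patient with progression by the investigator but not by BIRC who then starts new therapy also has no BIRC PFS event.

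TTR is a key secondary endpoint by both assessors. A response curve drawn under this rule can level off above the ORR reported beside it, in which the same patients are non-responders.

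**Working it through.** **The plan's own figures.** The documents give no figure for TTR. The Simon operating characteristics (SAP Table 2-3) reproduce by exact binomial calculation: 0.6828/0.0487 at a true ORR of 35% and 0.0631/0.9000 at 50%, against the stated 0.683/0.049 and 0.063/0.900. They do not involve TTR and do not change.

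**Who is misclassified**

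| Non-responder's situation | PFS event? | Can still respond? | TTR rule applied |
|---|---|---|---|
| Documented PD or death, fewer than two missed scans, no new therapy | Yes | No | Maximum follow-up (correct) |
| New therapy before documented PD (row F) | No | No | Last adequate scan (wrong) |
| PD or death after two or more missed scans (row C2) | No by Table 2-1; yes by the TTR parenthesis | No | Depends on the reading |
| Progression-free, still being scanned, no new therapy | No | Yes | Last adequate scan (correct) |

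**Size.** Let c be the share of all patients who are non-responders wrongly censored early. The documents do not give c, so these inputs are assumptions: c = 5%, ORR = 60%, and responses split 70/20/10% over weeks 8, 16 and 24 (the 8-week scan schedule is from the protocol). As shares of all patients, responses are 0.42, 0.12 and 0.06. The other non-responders (0.35) are held to maximum follow-up. Responses precede censoring at ties.

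- All non-responders held: S = 0.58 × (0.46/0.58) × (0.40/0.46) = 0.40, so 1-KM = 60.0%, equal to ORR.
- Censored before any post-baseline scan: 1-KM = ORR/(1-c) = 0.60/0.95 = 63.2%, excess **+3.2 points**.
- Censored at week 8: the risk set falls from 0.58 to 0.53. S = 0.58 × (0.41/0.53) × (0.35/0.41) = 0.383, 1-KM = 61.7%, excess **+1.7**.
- Censored at week 16: the risk set falls from 0.46 to 0.41. S = 0.46 × (0.35/0.41) = 0.393, 1-KM = 60.7%, excess **+0.7**.
- Censored at or after week 24, the last response: S = 0.40, excess **zero**.

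**Check with whole patients.** Take 53 responders of 105 (50.5%) and vary the share of responses at week 8 from 85% to 50%, with the rest at later 8-week scans.

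| Wrongly censored | Before any scan | Week 8 | Week 16 |
|---|---|---|---|
| 5 | 53/100 = 53.0% | 51.2–52.2% | 50.8–51.7% |
| 10 | 53/95 = 55.8% | 52.0–54.2% | 51.1–53.1% |

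**Direction.** Moving a non-responder from maximum follow-up to an earlier date can only shrink later risk sets. 1-KM therefore rises or stays the same; it never falls.

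**The case against.** The case on the other side is substantial.

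1. *The TTR section itself plans no curve.* Its summary is confined to responders and is untouched by how non-responders are censored. The DOR, PFS and OS sections each specify Kaplan-Meier tables and graphs with time points; TTR does not. This stands, but it does not dispose of the point: the protocol and SAP 4.6.3 both plan the curve, and a censoring rule for non-responders has no purpose without one.
2. *Row C2 is ambiguous.* A reader might infer that a dead patient is definitely censored as still able to respond. The documents do not settle that. The parenthesis in the TTR rule, read literally, sends anyone who progressed or died to maximum follow-up; only the Table 2-1 definition of a PFS event does the opposite. The new-therapy group has no such ambiguity.
3. *The curve need not exceed ORR.* A reader might infer that it always does. It does so only if an affected patient is censored before the last observed response. Imaging at the end-of-treatment visit and continued scanning after stopping without progression (protocol 7.2.1.2) tend to make the last scan later. The TTR rule also does not say whether scans after new therapy count as adequate; if they did, the excess would shrink further.
4. *Phase I offers no estimate of c.* Protocol 1.2.1.2.2 states "Post-baseline tumor measurements are available for 104 of the 114 response-evaluable patients", and a reader might take the missing 10/114 = 8.8% as c, giving 0.60/0.912 = 65.8%. That is unsupported. The figure counts absent measurements, not new therapy or late progression. It comes from patients of whom 79 of 114 had prior crizotinib, and it may include early deaths, which this SAP handles correctly.
5. *Appendix II is not visible.* Protocol 10.5.1 refers to it for TTR censoring, so it could not be checked. SAP 2.8.1 nevertheless states its own rule.
6. *Nothing inferential depends on TTR.* It has no hypothesis, power calculation or decision rule. This stands and sets the severity.

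**Conclusion.** The point holds for non-responders who start new anticancer therapy before documented progression: the stated reason for censoring them contradicts the SAP's own rule for best overall response. For progression or death after two or more missed scans it holds only on the Table 2-1 reading, and the wording should be made unambiguous.

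The consequence is that a Kaplan-Meier TTR curve can overstate the proportion responding, never understate it. Under the stated assumptions (c = 5%, ORR 60%, 70/20/10% timing) the excess runs from zero to 3.2 points, depending on when the affected patients had their last adequate scan. The true c and those scan dates are unknown from the documents. The primary ORR test, its operating characteristics and the responders-only TTR summary are unaffected. This is a minor point on a descriptive key secondary endpoint.

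**What to change.** In SAP 2.8.1 (Time to response), censor at maximum follow-up every non-responder who has progressed, died or started further anticancer therapy, whatever the PFS censoring status. Keep censoring at the last adequate assessment for the remaining non-responders only. Reporting the Aalen-Johansen cumulative incidence of confirmed response, with these events as competing, would serve equally well.

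In the same edit, reconcile the responders-only summary in SAP 2.8.1 with the Kaplan-Meier plan in SAP 4.6.3 and protocol 10.5.1 by stating whether a TTR curve will be produced. If it is dropped, record that in SAP Table 3-1.

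The cost is one sentence and one censoring flag, and the displayed curve may be slightly lower. The change does not guarantee that the curve levels off at ORR: non-responders who withdraw or are lost without progression would still be censored at their last scan, yet they count as non-responders in ORR. A table footnote can say so.
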